In addition: The data on 1) Physical Exam; 2) Clinical Laboratory Values 3) Arterial Blood Gas; and 4) Vital Signs, including heart rate, blood pressure and oxygen saturation, at the different time-points prior, during and post the study drug administration will be collected to evaluate the effects of Regadenoson on these patients. The data on the ventilator parameters, the length of stay on ventilator, and the length of stay in ICU and/or hospital will also be collected during the post follow up to evaluate the efficacy of Regadenoson in these moderate to severe Covid-19 patients.

Due to the mixture of the moderate and severe COVID-19 patients with various baseline severity levels, we will record pertinent patient information, such as age, sex, race, symptoms, signs, saturation of oxygen, medications, treatments, days of illness, comorbidities, chest X-ray imaging, and baseline severity (such as, on oxygen, on ventilator, on ECMO etc.) prior to Regadenoson infusion. We will also record whether each participated patient is treated with additional COVID-19 therapies. When we analyze the effects of Regadenoson on COVID-19, we can subgroup these patients and conduct primary efficacy analysis and propose appropriate methods of covariate adjustment.

Study Design:

This is a single center, randomized, phase 2 study to evaluate the safety, tolerability, and efficacy of Regadenoson for the treatment of moderate to severe adults with COVID-19. Patients will be followed up for 30 days from the start of study drug administration.

Estimated sample size: 40

Estimated accrual period: 18 months

Allocation: Randomized

Masking: Double-blind, placebo-controlled

Study Duration for each subject: 30 days

Study Treatments:

Regadenoson will be given intravenously as a 5µg/kg loading dose (a dose less than 400µg) over 30 minutes, followed by a continuous slow infusion (1.44µg/kg/hour) with

the use of a pediatric infusion pump for 6 hours. The saline will be used as placebo controls.

Eligibility Criteria

Inclusion Criteria:

- 1. 18 years of age or older
- 2. Laboratory-confirmed COVID-19+ by RT-PCR
- 3. Moderate to Severe COVID-19 patients according to FDA's COVID-19 treatment guideline on Management of Persons with COVID-19:
- Verbal or written informed consent must be obtained from patient or LAR (Legally Authorized Representative) before any study procedure is performed.

Exclusion Criteria:

- 1. Pregnant or breastfeeding women

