- 2. Subject has signs or symptoms of acute myocardial ischemia or has required a cardiac intervention within the past 90 days.
- 3. Subject with chronic cardiac conditions including non-vascularized coronary artery disease, heart failure, valvular disease, and cardiomyopathy.
- 4. Subject has an acute or chronic cardiac arrhythmia such as Sinoatrial (SA) or Atrioventricular (AV) Nodal Block/dysfunction, bradycardia, a permanent pacemaker, an internal defibrillator, or Atrial Fibrillation/Atrial Flutter requiring treatment or observation.
- 5. Subject has history of hypotension (sustained systolic blood pressure < 80 mmHg)
- 6. Subject has a history of severe hypertension not adequately controlled with antihypertensive medications (Systolic blood pressure ≥ 200 mmHg and/or Diastolic blood pressure ≥ 110 mmHg)
- Subject has moderate or severe renal impairment as well as subject with end stage renal disease (defined as GFR < 60 mL/min/1.73 m2)
- 8. Subject has a history of clinically overt stroke within the past 3 years
- 9. Subject with a history of seizure disorder
- 10. Subject has pre-existing respiratory conditions, most notably asthma or chronic obstructive pulmonary disease or emphysema.
- 11. Subject with respiratory failure for greater than 72 hours. Defined as the continuous use of mechanical ventilation, HFNC >20L/min, CPAP, and/or ECMO. (CPAP use due to obstructive sleep apnea is acceptable).
- 12. Subject who is being treated with chronic anti-coagulation or anti-platelet therapy (prophylactic aspirin is acceptable)
- 13. Subject who is receiving or has received within 30 days any other investigational agents as part of a research study.

- 14. Subject who has received theophylline or aminophylline within 12 hours of study dosing
- 15. Subjects who are currently taking or have taken Persantine and/or Aggrenox within 5 days
- 16. Subjects who have any other clinical conditions that in the opinion of the investigator would make the subject unsuitable for the study.

Safety Assessments:

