This study will be conducted in 2 cohorts. Our ongoing phase 1 trial with slow infusion of Regadenoson (1.44micrograms/kg/hour) in lung transplant patients study showed no obvious dose limiting toxicity. Safety assessments (vital signs, Pulse oximetry and Arterial Blood Gas, laboratory studies, electrocardiograms, etc.) will be performed on a schedule commensurate with the level of care and the identified potential risk of the study drug during Regadenoson infusion and 12 hours post infusion. Given the cardiac risk with Regadenoson, we will continue cardiac monitoring during the infusion of Regadenoson, and EKGs daily or as needed, and cardiac markers only if cardiac symptoms occur. To monitor potential platelet aggregation effects, labs (PT, PTT, INR, platelets, D-Dimer, and thromboelastography (TEG)) will be drawn prior to the infusion and on post infusion day 1. Patients who receive anti-clotting medications during Regadenoson infusion or within 6 hours of the end of infusion will be checked for clotting time and if necessary, anti-coagulant administration will be reduced or stopped. In addition, we will have a pregnancy test for patients who may have potential risk with a urine sample before study drug administration. Patients with a negative result will be enrolled. We will ensure that protections for women of childbearing potential align with International Council on Harmonization M3 R2 guidelines for highly effective methods of contraception.

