In cohort 1, we will enroll patients to test the safety, tolerability and toxicity in moderate to severe COVID-19 patients. Initial subjects in cohort 1 will receive a loading dose of 5.0 μ g/kg (not to exceed 400 μ g) over 30 minutes followed by a low dose infusion of 1.44 μ g/kg/hr. Toxicity of Regadenoson treatment will be graded by using the Common Terminology Criteria for Adverse Events (CTCAE) Criteria version 4.03 in this trial. If two dose limiting toxicities occur at a loading dose of 5.0 μ g/kg then the loading dose will be halved to 2.5 μ g/kg and enrollment will continue. If two dose limiting toxicities occur at a loading dose of 2.5 μ g/kg then the Data and Safety Monitoring Board (DSMB) will convene to determine if the study should continue and omitting the loading dose may be considered. Alternatively, the DSMB will convene after 5 out of 5 patients or 5 out of 6 patients tolerate a given loading dose to make a determination on moving forward to cohort 2. Otherwise, the trial will be terminated. (please see the details in the Detailed DSMB Plan section)

The sickle cell trial and our phase 1 trial in lung transplant patients did not show any renal/hepatic toxicity. Because COVID-19 itself may cause renal injury, we will closely monitor the renal and hepatic function of these patients per their standard of care. To assess safety of each subject, we will tabulate sequentially the number of participants

who unexpectedly experience serious cardiovascular side effects or persistent (> 30 min) intolerable side effects. If at any point in the accrual, the posterior probability exceeds 90% that the risk of at least one serious side effect for participants in the Regadenoson arm is more than 10 percentage points greater than in the standard care arm, we will stop the trial.

Adverse Event (AE) Recording and Reporting:

All adverse events will be collected starting at time of consent through POD 30. Adverse events will be recorded on a case report form and will be assessed for seriousness, severity, attribution and expectedness by the site Principal Investigator. A serious cardiovascular side effect is defined as a sustained change (> 5 minutes) in systolic blood pressure >30 mm Hg or systolic blood pressure <75 mm Hg, tachycardia >130 bpm, or bradycardia <40 bpm.

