Regadenoson, the proposed drug in this proposal, is FDA approved agent for 1) Radionuclide myocardial perfusion imaging, 2) Phase II clinical trial in adult sickle cell disease patient (above reference #15), 3) Our phase I clinical trial in lung transplantation (IND# 062862, above reference #30). In the trial 1), Regadenoson (400 micrograms) was given intravenously within 30 seconds. In trials 2) and 3), Regadenoson was administrated with low dose, slow infusion (1.44micrograms/kg/hour) for up to 12 hours. No dose limiting toxicity was observed in these trials. Therefore, we anticipate the dose we are going to use in these moderate to severe COVID-19 patients in this proposal will be safe. The labeling of Regadenoson is attached.

Results For In Vitro and In Vivo Toxicology: Regadenoson was negative in the Ames bacterial mutation assay, chromosomal aberration assay in Chinese hamster ovary (CHO) cells, and mouse bone marrow micronucleus assay. Long-term animal studies have not been conducted to evaluate LEXISCAN's carcinogenic potential or potential effects on fertility. Minimal cardiomyopathy (myocyte necrosis and inflammation) was observed in rats following single-dose administration of Regadenoson. Increased incidence of minimal cardiomyopathy was observed on day 2 in males at doses of 0.08, 0.2 and 0.8 mg/kg (1/5, 2/5, and 5/5) and in females (2/5) at 0.8 mg/kg. In a separate study in male rats, the mean arterial pressure was decreased by 30 to 50% of baseline values for up to 90 minutes at Regadenoson doses of 0.2 and 0.8 mg/kg, respectively. No cardiomyopathy was noted in rats sacrificed 15 days following single administration of Regadenoson. The mechanism of the cardiomyopathy induced by Regadenoson was not elucidated in this study but was associated with the hypotensive effects of

Regadenoson. Profound hypotension induced by vasoactive drugs is known to cause cardiomyopathy in rats.

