All COVID-19 clinical research studies at the medical center are overseen by the institution's COVID-19 task force committee that helps organize the screening of COVID-19 patients for study enrollment. They have instituted a daily research huddle to facilitate this process and direct potential study subjects to the most appropriate clinical trials. All active studies are invited to this meeting where the newly admitted/diagnosed COVID-19 patients are discussed and presented for consideration of enrollment in clinical trials. This group of clinicians and investigators has been conducting this meeting since the Spring 2020 and thus far it has been a very successful mechanism by which patients are enrolled into clinical trials in a fair and clinically relevant approach. We will have a representative from our study team attend this meeting each day and do not anticipate any barriers or conflicts related to competing clinical trials.

Consent Forms and the Consenting Process

Consent forms will be written in accord with 21 CFR 50 and will be reviewed and approved by each institutions IRB prior to use. Subjects or legally authorized representatives (LARs) should be educated separately about the risks associated with COVID-19. Informed consent will be obtained from each participant or LAR prior to conducting any study-specific procedures.

Since COVID19 positive patients are in isolation rooms, discussion of the study is more complicated.

If the patient is alert and not intubated, the consent form could be presented to the patient in 2 ways; either physically by the nurse or electronically (patient can view via iPad). The PI will then call into the patient room and go over the study with the patient and answer any questions they may have.

The patient will be evaluated to determine if they have the capacity to consent to the study. This evaluation will be documented. If the patient is intubated or otherwise incapacitated, the legally authorized representative (LAR) will be identified and their relationship to the patient documented. PI will call the LAR to discuss the study. The research staff will send the consent form electronically to the LAR, and the consent

process will occur over the phone, since there may be a no visitor policy in place for COVID patients. Verbal consent will be accepted.

Maintenance of Study Documents

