- * Not required, but to be recorded if available.
- 1 If female and of childbearing age.
- 2 If enrolled in the randomization arm.
- 3 Record available medications and vital signs including heart rate, blood pressure, oxygen saturation, respiratory rate
- 4 Laboratory tests includes CBC with differential count, chemistries with creatinine, ALT, AST, total bilirubin, ESR, LDH, CK when available. PT, PTT, INR, TEG, CRP, and D-Dimer are required prior to infusion and on post infusion day 1.
- 5 Required at baseline and D1 if arterial line present.
- 6 For open enrollment and Randomized subjects: blood samples will be collected prior to infusion, immediately after the load dose, 4 hours into the low dose infusion, and post infusion day 1.

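### Cardiac markers are drawn only on symptoms, so the asymptomatic, ECG-negative enzyme rise that Table 1 grades will not be systematically ascertained or comparable between arms

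*Combined protocol and SAP*

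**What the plan says.** The Safety Assessments section acknowledges a cardiac hazard and sets the surveillance: "Given the cardiac risk with Regadenoson, we will continue cardiac monitoring during the infusion of Regadenoson", with "EKGs daily or as needed, and cardiac markers only if cardiac symptoms occur". Grading follows a published scale: "Toxicity of Regadenoson treatment will be graded by using the Common Terminology Criteria for Adverse Events (CTCAE) Criteria version 4.03 in this trial". Table 1 sets out the grades.

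- Row 10 (myocardial infarction), Grade 2: no symptoms, enzymes minimally abnormal, no ischemic ECG evidence.
- Row 7 (heart failure), Grade 1: no symptoms, with an abnormality in a laboratory value such as BNP or on cardiac imaging.

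In Table 2, EKG/cardiac monitoring is marked at screening and D1; later entries are recorded only if available. Note 4 lists CK among tests to record when available and names no troponin or BNP. The same note makes a second group of tests mandatory (PT, PTT, INR and TEG among them): "CRP, and D-Dimer are required prior to infusion and on post infusion day 1".

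On who may be enrolled, the Synopsis mentions "baseline severity (such as, on oxygen, on ventilator, on ECMO etc". Exclusion criterion 11 removes only a "Subject with respiratory failure for greater than 72 hours". The consent section provides that "If the patient is intubated or otherwise incapacitated, the legally authorized representative (LAR) will be identified".

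The toxicology summary reports: "Minimal cardiomyopathy (myocyte necrosis and inflammation) was observed in rats following single-dose administration of Regadenoson".

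**The concern.** A grade defined by an enzyme result without symptoms can be assigned only if someone without symptoms is tested. Under the written trigger, nothing prompts that test. Three consequences follow.

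1. **Ascertainment.** A low count of marker-defined events would partly reflect how seldom markers were drawn. Safety comes first in the primary objective, and the Sample Size section gives safety analysis priority so that the trial can expand to more sites.
2. **Comparability of arms.** Testing depends on an event after treatment. The Sample Size section names dyspnea among the intolerable side effects. If regadenoson provokes it, and it is read as a cardiac symptom, treated patients could be tested more often, and enzyme rises due to COVID-19 would be found preferentially in that arm. Blinding does not remove this, because the trigger is the symptom itself.
3. **Attribution.** Without a required pre-infusion value, a raised result cannot be classed as new or pre-existing.

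Intubated or incapacitated participants may be unable to report the symptom that starts the process.

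**Working it through.** The plan gives no figure for this point, so there is none to reproduce. The main check is to set the provisions side by side.

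**Step 1. Which scheduled procedure could yield Table 1 row 10, Grade 2?**

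| Procedure | Where | Can it yield the grade? |
|---|---|---|
| Cardiac markers | Safety Assessments | Not prompted: they require symptoms, and the grade has none |
| EKG, screening and D1, daily or as needed | Safety Assessments; Table 2 | No: the grade requires that ischemic changes be absent |
| Cardiac monitoring during infusion | Safety Assessments | Shows rhythm and haemodynamic change, not an enzyme value |
| CK | Table 2, note 4 | Only if it happens to have been done |
| Mandatory tests before infusion and on post-infusion day 1 | Table 2, note 4 | No: coagulation tests, D-Dimer and CRP |
| Research blood | Table 2, note 6; Brief Assay Descriptions | Paired samples exist, but no cardiac marker is named |

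No scheduled test supplies the grade. Row 7, Grade 1 is a related but weaker case, since it can also be met by imaging. The acute coronary syndrome grades are all symptomatic and are not affected.

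**Step 2. Can every participant trigger the test?** Baseline severity may include a ventilator or ECMO, the exclusion applies only beyond 72 hours, and consent through a representative is foreseen for intubated patients. Some eligible patients may therefore be unable to report symptoms. The documents do not say how many.

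**Step 3. Does it reach the pause and stop rules?** The AE Recording section defines a serious cardiovascular side effect by blood pressure and heart rate only. An enzyme rise would not enter that component even if measured. I found no definition of dose-limiting toxicity in the available text, so the effect on the cohort 1 rule cannot be settled.

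**Step 4. Scale, for illustration.** Input: 40 participants randomized equally (Sample Size section), so n = 20 per arm. Assumption: a true rate p of silent, marker-positive injury, which the documents do not give. The chance that sampling everyone in one arm shows at least one case is 1 − (1 − p)^20:

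- p = 5%: 1 − 0.95^20 = 0.642
- p = 10%: 1 − 0.90^20 = 0.878
- p = 20%: 1 − 0.80^20 = 0.988

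This is the chance of seeing a case, not of attributing it to the drug. If 20% of controls and 30% of treated patients had raised markers (both assumed), a one-sided Fisher exact test at 5% with 20 per arm has power of about 11%.

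**Step 5. Weight of the rat finding.** The toxicology section gives effects at 0.08 to 0.8 mg/kg, that is 80 to 800 µg/kg. The planned total per patient is 5 + 6 × 1.44 = 13.64 µg/kg. The ratios are 80/13.64 = 5.9 and 800/13.64 = 58.7, per kg and without species scaling.

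**The case against.** **Table 1 is a grading scale, not a surveillance schedule.** Stroke Grade 1 covers findings seen only on imaging, yet nobody would infer routine brain imaging. This is fair: a grade that is reached only incidentally is not by itself an error. What stands is narrower. The plan singles out cardiac risk, and for this grade the sole marker provision is tied to a condition that the grade excludes.

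**Silent injury could be found in other ways.** A reader might infer that it cannot be detected at all. The documents do not support that. Monitoring, EKGs, incidental CK and standard-of-care tests may reveal some of it. The gap is in systematic ascertainment, chiefly of ECG-negative rises.

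**Few patients may be unable to report symptoms.** A reader might also infer that many are. No share is given, and the Sample Size section expects 80% to 90% alive and free of respiratory failure through the trial, which suggests a minority. Only the possibility stands.

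**The rat data do not predict harm here.** The doses were far higher per kg, the lesion was associated with hypotension, and none was noted at day 15. Hypotension is covered by the serious cardiovascular definition. I therefore place no weight on this finding as an estimate of human risk.

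**The population is selected.** Acute ischemia, recent cardiac intervention, heart failure, cardiomyopathy and arrhythmia are exclusions. That may lower the rate, but it does not supply a test.

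**The added data would be non-specific.** COVID-19 can raise markers in both arms, and power is low. This stands as a limit on what the fix can show.

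**Conclusion.** The concern holds as a gap in ascertainment. As written, the plan will not systematically find the asymptomatic, ECG-negative enzyme rise that it grades, requires no baseline value to interpret one, and lets testing vary with symptoms after treatment.

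Its size cannot be fixed from the documents; the detection probabilities in the working rest on assumed rates. The stronger conclusion, that regadenoson's cardiac safety would be declared on no evidence, is not supported: the plan nowhere says that an absence of marker events will be reported as cardiac safety, and haemodynamic events remain monitored. The cardiovascular part of the pause and stop tabulation is unaffected.

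This is an inexpensive improvement that should be made, not a flaw that invalidates the trial.

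**What to change.** Reconcile the marker provision in Safety Assessments with Table 1 row 10 and Table 2 note 4:

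- Add one cardiac marker assay, for example troponin, to note 4's list of tests required before infusion and on post-infusion day 1, for every participant in both arms.
- Keep the symptom-triggered test as an addition, and flag those results so that scheduled and triggered values can be tabulated separately.
- Report the pre-infusion value, the day 1 value and the change from baseline by arm, descriptively, with the number tested in each arm. State that no formal comparison is intended.

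Cost: 40 participants × 2 samples = 80 assays, at draws that are already mandatory, so no extra venipuncture is needed. Any participants enrolled outside the 40 would add two assays each. No dose or treatment rule changes. The downside is non-specific elevation from COVID-19 in both arms; values confined to two time points will also miss rises that appear later.

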The primary outcome is the proportion of patients alive and free of respiratory failure through the 30-day trial. The total sample size of 40 participants will be randomized equally between the usual care and Regadenoson groups, using a randomly permuted block design, with random block sizes of 2 and 4. This plan will be generated by the study statistician. Within each group, the primary outcome proportion can be estimated with a standard error of no more than 11 percentage points; the difference between the groups can be estimated with a standard error that is no more than 16 percentage points. These calculations are based on the most conservative estimate in terms of standard error, using a proportion of 50% in each group. If, as expected, the proportions in each group are greater, such as 80% in usual care and 90% in the Regadenoson group, the difference can be estimated with a standard error of 11 percentage points. While these are relatively large standard errors, they are adequate to meet the objective suggested by the IND review, providing estimates of outcome proportions to be used in a larger trial.

To assess safety, the DSMB statistician will tabulate sequentially the proportion of participants in each group who unexpectedly experience serious cardiovascular side effects or persistent (> 30 min) intolerable side effects, based on clinical experience with Regadenoson. Intolerable side effects include headache or dyspnea. If the lower bound of a one-sided 80% confidence interval for the difference in proportions exceeds 10%, we will pause the trial, examine the adverse event profiles, and consider modifying dosing. With this rule, if the true proportion of patients who experience serious side effects is 20% in each group, there is a 16.5% chance that the trial will be paused; if the

true proportion with Regadenoson is 40%, there is a 58% chance the study will be paused.

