APPENDIX A: NIAID 8-Point Ordinal Scale for COVID-19

The ordinal scale is an assessment of the clinical status at the first assessment of a given study day. The scale is as follows:

- 1. Death;
- 2. Hospitalized, on invasive mechanical ventilation or extracorporeal membrane oxygenation (ECMO);
- 3. Hospitalized, on non-invasive ventilation or high flow oxygen devices;
- 4. Hospitalized, requiring supplemental oxygen;
- 5. Hospitalized, not requiring supplemental oxygen, requiring ongoing medical care (COVID-19 or otherwise);
- 6. Hospitalized, not requiring supplemental oxygen, and no longer requires ongoing medical care (e.g., patient still admitted for isolation purposes only).
- 7. Not hospitalized, limitation on activities;
- 8. Not hospitalized, no limitations on activities.

Table 1, Detailed Grading Scales of Toxicity of Regadenoson

	CTCAE v4.0	Grade 1	Grade 2	Grade 3	Grade 4	Grade
1	Acute coronary syndrome	-	Symptomatic, progressive angina; cardiac enzymes normal; hemodynamicall y stable	Symptomatic, unstable angina and/or acute myocardial infarction, cardiac enzymes abnormal, hemodynamically stable	Symptomatic, unstable angina and/or acute myocardial infarction, cardiac enzymes abnormal, hemodynamically unstable	5 Death
2	Atrial fibrillation	Asymptom atic, interventio n not indicated	Non-urgent medical intervention indicated	Symptomatic and incompletely controlled medically, or controlled with device (e.g., pacemaker), or ablation	Life-threatening consequences; urgent intervention indicated	Death
3	Atrial flutter	Asymptom atic, interventio n not indicated	Non-urgent medical intervention indicated	Symptomatic and incompletely controlled medically, or controlled with device (e.g., pacemaker), or ablation	Life-threatening consequences; urgent intervention indicated	Death
4	Atrioventric ular block complete	-	Non-urgent intervention indicated	Symptomatic and incompletely controlled medically, or controlled with device (e.g., pacemaker)	Life-threatening consequences; urgent intervention indicated	Death
5	Atrioventric ular block first degree	Asymptom atic, interventio n not indicated	Non-urgent intervention indicated		-	-
6	Cardiac arrest	-	-	-	Life-threatening consequences; urgent intervention indicated	Death
7	Heart failure	Asymptom atic with	Symptoms with mild to	Severe with symptoms at rest	Life-threatening consequences;	Death

		laboratami	madarata	or with minimal	urgont	
		laboratory	moderate	or with minimal	urgent	

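### Serious Table 1 cardiac events and stroke do not count in their own right in the safety boundary, so the stated 58% pause probability does not cover an excess of them

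*Combined protocol and SAP*

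**What the plan says.** Safety Assessments and Sample Size and Statistical Analysis both tabulate participants "who unexpectedly experience serious cardiovascular side effects or persistent (> 30 min) intolerable side effects".

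- **Cardiovascular part.** Adverse Event (AE) Recording and Reporting, in the synopsis, states: "A serious cardiovascular side effect is defined as a sustained change (> 5 minutes) in systolic blood pressure >30 mm Hg". It then adds systolic pressure below 75 mm Hg, "tachycardia >130 bpm, or bradycardia <40 bpm". Nothing else is listed.
- **Symptom part.** Sample Size and Statistical Analysis states: "Intolerable side effects include headache or dyspnea".
- **Stop rule** (Safety Assessments). The trial stops once the following excess over control has a posterior chance above 90%: "the risk of at least one serious side effect for participants in the Regadenoson arm is more than 10 percentage points greater".
- **Pause rule** (Sample Size and Statistical Analysis). "If the lower bound of a one-sided 80% confidence interval for the difference in proportions exceeds 10" percent, the trial is paused. The stated pause probabilities are 16.5% when the true event rate is 20% in each arm, and 58% when it is 40% on Regadenoson.
- **Toxicity list.** After Appendix A comes "Table 1, Detailed Grading Scales of Toxicity of Regadenoson". Its rows include acute coronary syndrome, myocardial infarction, AV block, atrial fibrillation and flutter, ventricular arrhythmia, cardiac arrest and stroke. They also include headache, acute kidney injury and bronchospasm.

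No section adds a Table 1 diagnosis, a CTCAE grade, a serious adverse event or a death to the boundary tally.

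**The concern.** The plan anticipates specific cardiac harms and stroke. It grades them in Table 1, refers to the drug's cardiac risk, and excludes patients with ischaemia, arrhythmia or a recent stroke. Yet the event that drives its numerical rules is a set of vital-sign limits plus persistent symptoms. A sustained 31 mm Hg change in systolic pressure counts. An infarction that Table 1 puts at Grade 3 with stable haemodynamics need not.

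What is at stake is how the boundary is read. These are the only numerical between-arm safety rules, and 16.5% and 58% are the only operating characteristics given. A board told that the boundary has not been crossed could take reassurance about harms that never entered the count.

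**Working it through.** **Inputs.** 40 participants, with "The total sample size of 40 participants will be randomized equally between the usual care and Regadenoson groups", so 20 per arm. Looks at 15, 25 and 40 enrolled come from Scheduling, Timing, and Organization of Meetings in the DSMB plan. That the pause rule is applied at exactly those looks is an assumption.

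**Rule.** Pause if d − 0.842 × SE > 0.10. Here d = p_R − p_C is the observed difference, Regadenoson minus control, and SE = √[p_R(1−p_R)/n_R + p_C(1−p_C)/n_C].

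**Step 1: reproduce the plan's figures.** Simulation of 400,000 trials:

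| Looks and split | 20% v 20% | 40% v 20% |
|---|---|---|
| Plan | 16.5% | 58% |
| 15/25/40, odd participant on Regadenoson (8:7, 13:12, 20:20) | 16.3% | 58.4% |
| 15/25/40, odd participant at random | 16.7% | 60.1% |
| Single look at 40 | 4.9% | about 44% |

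The stated figures fit the rule at the three DSMB looks. There is no arithmetic error.

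**Step 2: add events that the definition does not count.** Assume counted events in 20% of both arms. Add an independent excess e, on Regadenoson only, of Table 1 events that cross no limit and cause no persistent intolerable symptom. If these counted, the Regadenoson rate would be 1 − (1 − 0.20)(1 − e) = 0.20 + 0.80e. Looks are at 15/25/40 with the odd participant at random.

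| e | Rate if counted | Pause probability, current definition | Pause probability if counted |
|---|---|---|---|
| 5% | 24% | about 17% | 24% |
| 10% | 28% | about 17% | 32% |
| 20% | 36% | about 17% | 50% |
| 25% | 40% | about 17% | 60% |

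The third column is flat because the tally never sees the excess. The last row is the plan's own 40% v 20% case.

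**Step 3: one concrete data set.** Take 4/20 counted events on control at the final look.

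- 8/20 on Regadenoson: 0.20 − 0.842 × √(0.40×0.60/20 + 0.20×0.80/20) = 0.20 − 0.119 = 0.081. No pause.
- 9/20 on Regadenoson: 0.25 − 0.842 × √(0.45×0.55/20 + 0.20×0.80/20) = 0.25 − 0.120 = 0.130. Pause.

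Four counted events plus five stable infarctions or strokes in other Regadenoson patients would be 9/20 if all counted. Under the present definition the tally is 4 v 4.

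**Step 4: the cost of counting more.** Let b be the added background rate of newly counted events in both arms, independent of the 20%. The control rate becomes 0.20 + 0.80b.

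| b | Control rate | False-pause probability |
|---|---|---|
| 0% | 20% | about 17% |
| 5% | 24% | about 18% |
| 10% | 28% | about 19% |
| 20% | 36% | about 20% |
| 30% | 44% | about 21% |

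With b at 20% to 30%, detection of the same independent 20% excess falls from about 50% to about 44% and 41%.

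The posterior stop rule uses the same tally. The plan gives no prior, so no stop probability is computed for it here.

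**The case against.** Several stronger readings are tempting, and the documents do not support them.

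- **That Table 1 events never count.** Atrial fibrillation above 130 bpm counts. So does heart block below 40 bpm, or an infarction with systolic pressure below 75 mm Hg or a sustained change above 30 mm Hg. The symptom part uses the verb *include*, so headache and dyspnea are examples, and persistent infarct pain could qualify.
- **That a short cardiac arrest is excluded.** This holds only if the 5-minute condition governs every limit. In the text it is attached to the systolic change, and on that reading an arrest would meet the pressure or heart-rate limit at once. The wording is ambiguous.
- **That the plan ranks these harms highest.** It ranks no harms. Table 1 is a grading grid that also contains headache and first-degree AV block.
- **That grading matters only in cohort 1.** Dose-limiting toxicity is not defined, and CTCAE grading applies to the whole trial, so this cannot be shown.
- **That patients are unprotected.** Related serious adverse events and all deaths go to the DSMB within 7 days. The board reviews adverse events at each meeting with unblinded reports, and may pause or halt at any time. It also reviews the statistical monitoring plan, whose final version is kept with the charter and may add detail.

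The decision sentences also speak of serious side effects without the word cardiovascular, so a wider meaning is arguable. But the event to be tabulated is the narrow one.

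The illustration leans on independence. Arrest, ventricular fibrillation and unstable infarction will often cross a limit, and the exclusions remove many cardiac patients. At a 5% excess the gain is only from about 17% to 24%.

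These points narrow the concern to the numerical boundary. They do not remove it: board discretion carries no stated operating characteristics, and the definition as written leaves the stable events out.

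**Conclusion.** The point stands in a limited form. The boundary tally is defined by blood-pressure and heart-rate limits plus persistent intolerable symptoms, and it is not linked to Table 1, to the serious adverse event definition or to death. Serious cardiac events and stroke that cross no limit and produce no qualifying symptom are left out.

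The 16.5% and 58% are correct for the event as defined, but the 58% says nothing about an excess of the omitted events. The size of the gap depends on the rates assumed in Step 2, which the documents do not supply. Any overlap between Table 1 events and the vital-sign limits makes it smaller. The gap is in the numerical rules, not in safety oversight as a whole.

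**What to change.** In Safety Assessments, in the synopsis adverse event section and in Sample Size and Statistical Analysis:

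1. Reconcile the boundary event with Table 1 and the serious adverse event definition, so that serious cardiac events, stroke and deaths count in either arm. The sponsor and DSMB should specify the grades.
2. State which limits the 5-minute condition covers.
3. Recompute both pause probabilities for the new definition and state the looks used.

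Do this before boundary monitoring starts, because changing the event after seeing data by arm would undermine the rule.

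The cost is one definition and a re-run of the calculation. Expect a slightly higher false-pause figure: about 18–19% at an assumed 5–10% added background, and about 20–21% at 20–30%. The higher range is more likely if non-cardiac rows such as kidney injury or bronchospasm are included. Those rows would also need a recording change, because the DSMB plan leaves anticipated events such as wheezing and medication-related renal insufficiency unrecorded unless serious. Limiting the additions to cardiac events, stroke and deaths avoids most of this.
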